The population allocated to intervention comprises geriatric patients acutely admitted to the ED, Aarhus University Hospital (AUH) or transferred to one of the two geriatric wards at AUH. Subjects are included immediately on the day of admission at the ED, AUH and the Department of Geriatrics (wards 1 and 2), AUH, as shown in Fig. 1. Patients admitted to the ED at night and promptly discharged before enrollment to the intervention cohort can be performed the following day are not included. Likewise, patients to the control group are included immediately on the day of admission at the ED, Randers Regional Hospital (RRH), and at the medical wards 1, 2, 3 and 4, RRH. Patients transferred to other departments are excluded. Patients can only be included once. Enrollment and randomization to the intervention group are performed by therapists working in the ED or the geriatric wards. Enrollment to the control group is done by a Research Assistant. In the control group frailty screening is done by the PhD-student using a frailty screening tool based exclusively on data collected through medical records. The frailty screening tool will be validated by crosschecks performed by a blinded project Research Assistant. The results of the validation study will be analyzed and published during 2019.

Inclusion criteria:

- Aged 75 years or older
- Living within the municipality of Aarhus (except for the control group, see below)
- MPI-score = 2 (moderate frailty) or MPI score = 3 (severe frailty)

Exclusion criteria:

- Included in any other kind of follow-up schemes
- Declared terminally ill or undergoing palliative care at admission
- Admitted from one specific temporary nursing home with geriatric medical assistance (Vikærgården)
- Discharge or transfer to another department, including hospice
- MPI-score = 1 (low frailty)
- Discharged to one specific temporary nursing home with geriatric medical assistance (Vikærgården)
- The patient does not want a visit after discharge

Inclusion- and exclusion criteria to the control group are the same as for the two intervention groups, except that subjects eligible for the control group are living within the four municipalities of RRH: Randers, Favrskov, Norddjurs and Syddjurs.

Randomization

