The patients in the control group are discharged to usual care and do not receive early follow-up visits. Usual care features municipality services and optionally a GP home visit (see Appendix 2). Eligible control patients are consecutively included by a Research Assistant. The estimated level of frailty will be assessed by the PhD-student based on a MPI-screening tool fitted to be performed using only medical record data. This fitted tool will be tested and validated prior to the inclusion of the control group. Clinicians will be blinded to the result of the MPI-screening of the control subjects to ensure that discharge is performed in accordance with usual care.

Outcomes

The primary outcome is readmission within 30 days after discharge. Secondary outcomes are:

- Mortality 30 days after discharge and 90 days after admission
- Length of stay during primary admission and total length of stay including following readmissions
- Direct discharge from the Emergency Department
- Time at home before readmission
- Duration of readmission
- Physical functional status 30 days after discharge (Functional Recovery Score)
- Patient Related Outcome Measures as defined by a focus group of included patients and/or their relatives

Statistical analyses

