Power analysis is based on a pilot study performed from June to December 2017 using the method stated above, and earlier studies by Pedersen et al.(7,12), where patients selected by diagnoses associated with readmission were randomized to early geriatric follow-up visits or usual care. Readmissions were reduced from 23% to 12%. Data collected during the pilot study showed 13.7% readmissions in the Intervention group I compared to 8% readmissions in the Intervention group II. Based on the pilot study data, allowing a 5% drop-out rate and a 30-day mortality rate of 10%, the number of patients in each trial arm should be 758 in order to achieve a power of 90% and a level of significance of 5%. Data collected during the same pilot study showed a 90-day mortality rate of 20.6% in Intervention group I compared to 15.6 % in Intervention group II. To achieve a power of 80% and a level of significance of 5% with regards to mortality, the sample size of each arm should be 1,019, including a 5% drop-out rate.

Perspectives

This study may uncover a need for specialized and early efforts to support transfer of the frail elderly. We may find that some of the frail elderly are poorly supported by the present follow-up procedures, suggesting that comprehensive geriatric assessment and early follow-up intervention by a community nurse and a geriatric team should gain further currency in the future. This study may contribute to dimension health care services in the future. We hope to clarify the possible need for geriatric services outside university hospitals. The results are directly transferable to Danish regional hospitals and may be of importance in other Western countries.

Ethics

The study has been approved as a quality development project by the Regional Research Ethics Committee, Central Denmark Region (journal no. 197/2017), thereby no patient consent form is needed, and further referral to the committee not required. No patient will receive less than usual care, no extra treatment or examination will be applied, and no patient will be exposed to any additional risk because of the project. Participants may decline parts of or the entire intervention, including usual care, at any time. The project, which is a part of the national rate adjustment pool-project "Early post-discharge follow-up of the frail elderly – a intersectoral effort" in the Central Denmark Region, is approved by the Danish Data Protection Agency (journal no. 2012-58-006).

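### The night-discharge omission is written for Aarhus only, and the visit-refusal exclusion has no described way to work at Randers, so Study 2 may compare differently selected cohorts

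*Protocol*

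**What the plan says.** All references are to the Protocol; the December 2018 combined protocol and SAP reads the same on these points.

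**Night patients.** Study population states that night ED patients "promptly discharged before enrollment to the intervention cohort can be performed the following day are not included". The sentence names the intervention cohort and stands outside the bulleted criteria that the control group shares. The next sentence turns to Randers: "Likewise, patients to the control group are included immediately on the day of admission at the ED, Randers Regional Hospital". It does not say what happens to Randers patients who leave overnight.

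**How controls are found.** The Control group section states: "Eligible control patients are consecutively included by a Research Assistant". Frailty in controls is graded with a "frailty screening tool based exclusively on data collected through medical records". In Aarhus, therapists in the ED or on the geriatric wards enrol and randomise.

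**Refusal.** One exclusion criterion reads: "The patient does not want a visit after discharge". Control criteria are declared identical apart from municipality of residence, so on paper this one applies at Randers. The Control group section says, however, that controls "do not receive early follow-up visits".

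**Use of the comparison.** Under Design, Study 2 compares both randomised groups with the control cohort. Hypothesis 2 lists readmission, length of stay (LOS) and direct ED discharge among its outcomes. The Statistical analyses section plans correction for demographics and frailty, only if needed.

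**The concern.** A patient who arrives at the ED at night and is home before enrolment opens has, almost by definition, a very short stay and a direct discharge from the ED. A rule that removes such patients therefore selects on two of the outcomes in hypothesis 2. Applied at both hospitals, it merely narrows the population. Applied at one, it creates a difference in those outcomes that owes nothing to care.

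The written rule covers Aarhus only, and the enrolment methods make a real difference plausible. The MPI in Appendix 1A contains questions put to the patient, such as the mental status items, so an Aarhus patient must still be there to be scored. A Randers patient can be graded from the record.

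Refusal raises a similar difficulty. A patient can refuse the study visit only where it is offered. If Aarhus loses its refusers and Randers keeps the patients who would have refused, the cohorts differ in a characteristic that is not recorded for controls.

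Adjustment for demographics and frailty cannot bring back patients removed because they went home early or did not want a visit. Study 2 is the plan's only comparison with usual care.

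**Working it through.** The plan gives no figure for night discharges or refusals, so there is none to reproduce on this point. The sizes below are illustrations over stated ranges.

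**Inputs**
- Direct ED discharge p: 49% and 56%, from an earlier trial cited under Outcome measures. Its patients were selected by diagnosis, not by MPI.
- Share f of eligible Aarhus patients who are night-time direct discharges missed by enrolment: assumed 2%, 5% and 10%.
- Randers captures all of its own night discharges: assumed, and the most adverse case.
- No true effect of the intervention: assumed, to isolate the artefact.
- Cohort size n: 758 each, assumed. The plan gives no size for the control cohort. The figure of 758 is the readmission sample size per randomised arm, and it reproduces: 13.7% versus 8%, two-sided 5%, 90% power, with continuity correction gives 659, and 659 × 1.15 = 758.

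**Step 1, direct ED discharge.** Removing a share f, all of them direct discharges, changes the Aarhus rate from p to q = (p − f)/(1 − f). The approximate chance of a falsely significant gap in that direction is Φ(|p − q|/SE − 1.96), with SE = √{[p(1 − p) + q(1 − q)]/n}.

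| p | f | q | Gap (points) | Chance of false significance |
|---|---|---|---|---|
| 49% | 2% | 0.47/0.98 = 48.0% | −1.0 | 6% |
| 49% | 5% | 0.44/0.95 = 46.3% | −2.7 | 18% |
| 49% | 10% | 0.39/0.90 = 43.3% | −5.7 | 60% |
| 56% | 2% | 0.54/0.98 = 55.1% | −0.9 | 5% |
| 56% | 5% | 0.51/0.95 = 53.7% | −2.3 | 15% |
| 56% | 10% | 0.46/0.90 = 51.1% | −4.9 | 48% |

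**Step 2, comparison with the cited effect.** The cited change from 49% to 56% is 7 points. A false gap of that size needs f(1 − p)/(1 − f) = 0.07, so f = 0.07/(1 − p + 0.07). This gives 0.07/0.58 = 12.1% at p = 49% and 0.07/0.51 = 13.7% at p = 56%.

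**Step 3, plausibility.** At p = 49%, f = 2% means that 0.02/0.49 = 4% of all direct discharges are missed, and f = 10% means 0.10/0.49 = 20%.

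**Step 4, LOS.** The missed stays are among the shortest, so Aarhus LOS would look too long. The documents give only medians from the earlier trial (3 and 2 days), so the shift cannot be computed.

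**Step 5, refusal and readmission.** Let a share r refuse, with k times the readmission risk of accepters, and take 13.7% as the overall risk. Accepters' risk is a = 0.137/[(1 − r) + rk]. Over assumed ranges of r from 5% to 20% and k from 0.5 to 2, the extremes are 0.137/0.90 = 15.2% (r = 20%, k = 0.5) and 0.137/1.20 = 11.4% (r = 20%, k = 2). That is +1.5 to −2.3 points, so even the sign is open.

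**The case against.** A reader might infer that the fastest discharges are in the control cohort and can never be in the intervention cohort. The documents do not establish this. Only the frailty grading is record-based; enrolment at Randers is described as same-day, and the word that opens that sentence can be read as setting up a parallel procedure. Clinicians are blinded to the control MPI result so that discharge follows usual care, which makes most sense if screening comes before discharge. Baseline data, including the Functional Recovery Score, are to be collected in the whole study population before patients leave. No retrospective capture or round-the-clock cover is described at Randers, so the same patients may be missed at both sites. This objection stands: the plan is silent, and the bias is conditional. It does not remove the need to break the silence, because the omission bears directly on two outcomes.

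A reader might also infer that the refusal criterion can never exclude a control. It formally applies to them. Appendix 2 shows that usual care can include a community nurse or GP visit, that referral for the GP visit needs the patient's consent, and that screening for it is nominally standard on the Randers medical wards. Some controls may therefore decline a visit, but it is a different visit, proposed to a screened subset. What remains is that the plan describes no equivalent way to ascertain refusal there.

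Finally, the Ethics section says: "Participants may decline parts of or the entire intervention, including usual care, at any time". This could be taken to contradict the refusal exclusion. It need not: one can be an entry rule and the other a right after entry. What does stand is that the plan never says when refusal is recorded, although allocation is made on the day of admission and is open from then on.

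**Conclusion.** The point holds as a conditional risk to Study 2 that the plan leaves open, not as a demonstrated bias. As written, the night rule binds one site, and the refusal criterion has no described means of working equivalently at the other. If Randers captures every night discharge and the overnight share is 2% to 10%, direct ED discharge in Aarhus would be about 1 to 6 points too low and LOS too long, both against the intervention. If Randers misses the same patients, the night artefact largely disappears. With partial capture it lies in between. A gap as large as the cited 7-point effect would need a share of about 12% to 14%.

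Two further inferences are not supported. No direction of bias can be claimed for readmission, because the refusal effect could go either way and nothing is known about readmission among night discharges. Nor does the asymmetry reach the randomised comparison of I with II, where both groups come from the same Aarhus enrolment.

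**What to change.** 1. **One enrolment window.** State in Study population the hour at which Aarhus enrolment starts, and exclude control patients admitted at night and discharged before that hour. Check this on record time stamps. The plan lists dates of admission and discharge, so times of day must be added to the data taken from the records.
2. **Timing of refusal.** Apply the refusal exclusion only before randomisation. Keep anyone who declines later in the allocated arm and in the Aarhus cohort for intention-to-treat, with outcomes taken from records, and remove them only in the per-protocol analysis already planned.
3. **Counts.** Record at Aarhus the number of pre-randomisation refusers and of missed night discharges. State that refusal of the study visit is not elicited in controls. Use the counts in a Study 2 sensitivity analysis, replacing the assumed f and r above with observed values.

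The cost is a few lines of protocol text, a time-stamp check, slightly fewer controls, and some dilution of the intention-to-treat contrast by decliners. The plan does not say how the 30-day Functional Recovery Score is obtained, so it may be missing for decliners. A common window does not remove differences between the hospitals in night discharge practice, which remain a limitation of a non-randomised comparison. Deleting the refusal criterion altogether is not needed; it would change the randomised trial's target population and is a separate trade-off.

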All frail patients admitted to the ED and the Department of Geriatrics are randomized 1:1 to one of two different follow-up efforts prior to CGA performed during hospitalization. Thereby the intervention is randomly split into two groups:

- An intervention (I) consisting of CGA during hospitalization and early post-discharge follow-up care by a community nurse and a GP
- An intervention (II) consisting of CGA during hospitalization and early post-discharge follow-up care, including continued CGA and tailored follow-up care, by a geriatric team

The intervention cohort will be compared to a control cohort consisting of similar frail elderly who receive usual care without involvement of geriatric care during hospitalization and after discharge.

Hypotheses

- The geriatric team follow-up is as effective as a community nurse and GP follow-up measured by readmission, mortality, LOS, direct discharge from ED and physical functional recovery
- The effects of three transitional follow-up approaches (community nurse and GP; multidisciplinary geriatric team; usual care) are similar measured in terms of readmission, time at home, duration of readmission, LOS, direct discharge from ED, mortality and PROMs
- When stratified into subgroups with regards to level of frailty (moderate and severe) and type of dwelling, the geriatric team follow up is as good as community nurse and GP follow-up measured by readmission, mortality, LOS, direct discharge from ED and physical functional recovery

Methods

Design

The first study is conducted as a randomized controlled trial (RCT) using two different degrees of intervention. The second study is a cohort study where the two groups in the RCT are compared to an unexposed control group. The third study is sub-group analyses of the RCT data according to frailty status and type of dwelling.

Study population

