As shown in Fig. 2, all intervention group patients are allocated at the time of randomization on the day of admission to receive either early visit from the community nurse (I) or the multidisciplinary geriatric team (II). The randomization is stratified with regard to dwelling (living alone; cohabiting; nursing home) and number of drugs prescribed prior to

admission (0-3, 4-7, 8 or more drugs), and conducted using the randomization function in REDCap (49). Randomization is open throughout the whole admission with the purpose to enable early discharge planning.

Intervention I and II

Both intervention groups are assessed according to CGA, either by the geriatrician and the physiotherapist/geriatric nurse in the ED, or by a multidisciplinary team comprised of geriatricians, specialized nurses, physiotherapists and occupational therapists during hospitalization in the geriatric wards.

- Intervention (I): comprises early follow-up visit from the community nurse within 24 hours after discharge, and the possibility of consulting a nutritionist, thus supplementing usual care services including the possibility of consulting the patients' GP. Responsibility of treatment including implementation of suggested initiatives and any further assessment is handed over to the GP at discharge.
- Intervention (II): CGA is continued during early follow-up by the geriatric team. On weekdays visits are scheduled within 24 hours after discharge. For patients discharged during weekends or holidays, supporting telephone calls are provided by the geriatric team. If needed, the geriatric team nurse visits the patient. The concept of CGA in this stage does not differ from the above-mentioned. There are no standardized demands, but a part of the intervention can be to perform hospital services at home and continued treatment and diagnostics after discharge. The possible services provided by the geriatric team are further described in the geriatric team course description. The responsibility of treatment rests with the geriatric team until dispatch of the discharge summary. Patients then return to usual care. The geriatric team follow-up is planned to last a maximum of 7 days, yet allowing extension for as long as there is a need for services performed exclusively by the geriatric team as described in the geriatric team course description.

Control group

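### Two exclusion criteria carry no time limit and will usually be settled after open randomisation, while neither the intention-to-treat nor the per-protocol set is defined

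*Protocol*

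**What the plan says.** **Timing of allocation.** Under Objectives in the Protocol, frail patients "are randomized 1:1 to one of two different follow-up efforts prior to CGA performed during hospitalization". Under Randomization, "all intervention group patients are allocated at the time of randomization on the day of admission", and "Randomization is open throughout the whole admission with the purpose to enable early discharge planning".

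**Exclusions.** The list under Study population contains "Discharged to one specific temporary nursing home with geriatric medical assistance (Vikærgården") and "Discharge or transfer to another department, including hospice". The text above it repeats the second: "Patients transferred to other departments are excluded". Neither carries a time limit. Two other criteria do refer to baseline: terminal illness or palliative care is judged at admission, and the same nursing home also appears as a place of origin, "Admitted from one specific temporary nursing home with geriatric medical assistance (Vikærgården").

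**Analysis sets.** The Outcomes paragraph under Statistical analyses names intention-to-treat and per-protocol analyses in one sentence. It defines neither and does not say which is primary.

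**Outcomes.** The primary outcome is readmission within 30 days of discharge. Mortality is listed as "Mortality 30 days after discharge and 90 days after admission".

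The Combined protocol and SAP has the same text on all these points. Figs. 1 and 2, whose captions concern inclusion and exclusion, and randomisation, discharge and follow-up, are not in our copy.

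**The concern.** Discharge destination and transfer are mostly decided during the stay, after the patient has been allocated and while staff know the arm. An exclusion that rests on such a decision can remove a randomised patient for a reason that randomisation does not balance. If the arms differ in how many patients are removed, and those removed differ in risk from those kept, the I versus II comparison loses part of the protection of randomisation.

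Because neither set is defined, two analysts could build different primary datasets and both could cite the plan. One would keep every randomised patient; the other would first apply the exclusion list. That choice should not be open once outcomes are known.

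At stake are the primary outcome and 90-day mortality, the two outcomes for which the plan gives a sample size.

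**Working it through.** **1. The plan's sample sizes.** Inputs, from the Sample size section: readmission 13.7% v 8%, 90% power, 5% drop-out and 10% mortality; 90-day mortality 20.6% v 15.6%, 80% power, 5% drop-out; 5% significance, taken as two-sided. The continuity-corrected two-proportion formula gives:

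- Readmission: 659 analysable per arm; 659 × 1.15 = 757.85, i.e. 758 as stated.
- Mortality: 970 analysable per arm; 970 × 1.05 = 1,018.5, i.e. 1,019 as stated.

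The arithmetic is not at issue, and 659 and 970 are used below.

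**2. Bias from unequal removal.** Suppose there is no true effect and both arms have risk p. One arm loses a share x more of its patients, whose risk is r. The rate in that arm becomes

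(p − x·r) / (1 − x).

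The difference from p, divided by the pooled standard error √(2p̄(1−p̄)/n), gives z. Type I error is 1 − Φ(1.96 − z) + Φ(−1.96 − z). This is the test without continuity correction, with n held fixed.

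The documents give no removal rate. I assume x = 5%, equal to the plan's whole drop-out allowance falling on one arm. The plan does not link that allowance to these exclusions.

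*Readmission, p = 13.7%, n = 659:*

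| Risk in those removed | Rate in that arm | Bias (points) | Type I error |
|---|---|---|---|
| 8% (pilot, II) | 14.00% | +0.3 | 5.3% |
| 13.7% (pilot, I) | 13.70% | 0 | 5.0% |
| 23% (upper figure, earlier studies) | 13.21% | −0.5 | 5.8% |
| 30% (assumed) | 12.84% | −0.9 | 7.4% |

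The planned difference is 13.7 − 8 = 5.7 points. Over the 8-23% range, x = 3% gives 5.0-5.3% and x = 2% gives 5.0-5.1%.

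*90-day mortality, p = 20.6%, n = 970, x = 5%:*

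| Risk in those removed | Rate in that arm | Bias (points) | Type I error |
|---|---|---|---|
| 15.6% (pilot, II) | 20.86% | +0.3 | 5.2% |
| 20.6% (pilot, I) | 20.60% | 0 | 5.0% |
| 30% (assumed) | 20.11% | −0.5 | 5.8% |
| 50% (assumed) | 19.05% | −1.5 | 13.7% |
| 70% (assumed) | 18.00% | −2.6 | 30.6% |

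The 50% row in full: (0.206 − 0.05 × 0.50)/0.95 = 0.1905; difference 0.0155; standard error 0.0181; z = 0.855; type I error 13.7%. The planned difference is 20.6 − 15.6 = 5.0 points. No document figure gives the mortality of those removed. High values are shown because one criterion covers hospice, but a removed group made up largely of such patients is itself an assumption.

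**3. Dilution from keeping these patients.** Assume that 10% of analysed patients are retained and have no effect. The arm II rate becomes 0.9 × 8% + 0.1 × 13.7% = 8.57%, and the difference falls from 5.7 to 5.13 points. On the plan's continuity-corrected scale, power is

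Φ{[(|p₁ − p₂| − 1/n) − 1.96·√(2p̄(1−p̄)/n)] / √([p₁(1−p₁) + p₂(1−p₂)]/n)}.

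- n = 659, no dilution: (0.0555 − 0.0336)/0.0171 = 1.28, power 90.0%.
- n = 659, 10% diluted: (0.0498 − 0.0340)/0.0173 = 0.92, power 82.0%.
- n = 1,019/1.15 = 886: 96.6% falls to 91.9%.

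**The case against.** **The passages need not contradict each other.** A reader might infer that the exclusion list conflicts with intention-to-treat. The documents do not support that. Both analyses are named, and on a coherent reading patients who meet a discharge-related criterion after allocation stay in intention-to-treat and leave only the per-protocol set. This objection stands. What remains is that the plan does not say so, and the list is headed as exclusion from the study.

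**Some timing may be earlier than it looks.** Enrolment takes place partly in the ED, and some patients go home directly from there. A transfer, or a planned nursing-home destination, may sometimes be known before allocation. Figs. 1 and 2 may also settle the order. This stands too, which is why the point says usually and not always. It does not help patients admitted to a ward, whose destination is decided later.

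**No evidence that the arm drives the exclusions.** A reader might infer it from the open allocation, from the Protocol's statement that length of stay may depend on the planned follow-up, and from the rise in direct ED discharge (49% to 56%) that it attributes to geriatric team follow-up in earlier work. Those statements concern how soon patients leave hospital. None concerns discharge to the named nursing home, transfer or hospice. Differential removal is possible, not shown.

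**Refusal of a visit** is also on the list. It reads as a question asked at enrolment and matters here only if it arises after allocation.

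**Conclusion.** The point holds as a gap in definition with a possible bias. Two exclusions have no time limit, will usually be settled with the arm known, and would remove randomised patients if applied as written. The plan does not state which patients each analysis contains.

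Size and direction are unknown. For readmission, even a 5-point imbalance moves type I error only to 5.0-5.8% at the risks the documents give, so a claim of serious bias in the primary outcome would not be supported. It would be equally wrong to call the effect small for mortality: the result depends on the unknown risk in those removed and runs from 5.8% to 30.6% over assumed risks of 30% to 70%. All these figures rest on the assumed imbalance; with equal removal of patients at equal risk the error stays at 5%.

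The plan should be changed because the omission affects the main randomised comparison and is easily settled before the data are analysed.

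**What to change.** 1. Limit eligibility exclusions to facts known before the REDCap randomisation.
2. Define the intention-to-treat set as all randomised patients in their allocated arm, and name it as primary for I versus II.
3. Make later discharge to the named nursing home, transfer or hospice (and refusal, if it follows allocation) a reason for exclusion from the per-protocol set only. Report the numbers by arm and reason.
4. As a consequence, state how randomised patients who die before discharge enter the readmission analysis, and which discharge date starts the 30 days for transferred patients. The 90-day mortality outcome runs from admission and needs no such rule.

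**Cost.** The change is mainly to wording. Department and date of discharge, dwelling, readmission date and death date are already planned for the entire study population. They must also be collected for patients who would otherwise be dropped, and the 30-day Functional Recovery Score sought in them.

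The downside is possible dilution: under the 10% assumption, power falls from 90.0% to about 82% at 659 analysable per arm. Restoring 90% would take 827 analysable, or 827 × 1.15 = 951.05, i.e. 952 randomised per arm instead of 758. The plan does not say whether 758 or 1,019 is the target; at 1,019 the power would remain above 90%. There is no extra loss if the pilot rates already included such patients, which the sponsor can check. Show the per-protocol result and the retained share alongside.
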